Implementation of the dart-throwing motion plane in hand therapy after distal radius fractures: preliminary results

Study Protocol

Each subject read and signed an informed consent form pretrial. Then, personal information, upper limb range of motion (ROM), pain levels and functional tests were recorded by a hand therapist. The Sagittal group activated the wrist mostly in the sagittal plane while the research group activated the wrist also in the dart throwing motion (DTM) plane, via the dart splint orthosis applied by a hand therapist.

All of the subjects in both groups received 12 therapy sessions, 30 minutes each one, 2-3 times a week, during 6-8 weeks following the removal of the cast. Certified hand therapists used conventional treatment techniques during the sessions. Both groups were instructed to exercise at home, 3 times a day, 10 minutes per exercise session. The dart splint orthosis was fitted to the subjects in the DTM group on their first evaluation session. They were instructed to use the dart splint orthosis at home. For each 10-minute exercise session, they were asked to perform 5 minutes of radial-extension under resistance and then 5 minutes ulnar-flexion under resistance. In addition, this group was required to fill in a chart at the end of each practice session, throughout the intervention period. The evaluator performed weekly phone calls to remind the DTM group to fill these out. The Sagittal group was instructed to perform at home active wrist motion similar to that practiced during the supervised therapy sessions. The prescribed instructions were similar to the exercises performed during the sessions. At the completion of the treatment, the subjects were reexamined by the same evaluator.

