Implementation of the dart-throwing motion plane in hand therapy after distal radius fractures: preliminary results

Statistical Analysis Plan

Radiological measurements were performed considering radial height, radial inclination, volar tilt, intra-articular step-off and ulnar variance, both preoperatively and postoperatively. For each subject, the researchers calculated the residual deficit in all of the parameters between the evaluation post treatment and the evaluation at baseline (percentage = $100 - \text{post} / \text{pre} \cdot 100$). For the pinch and grip strength tests, measured post treatment, the researchers calculated the percentages of the values of the injured hand in relation to the uninjured hand (percentage = $\text{injured} / \text{uninjured} \cdot 100$).

Statistical analyses were performed in IBM SPSS software, v25 (IBM, Armonk, NY). The Shapiro-Wilk test of normality was used on all acquired variables. The majority of variables were not normally-distributed so a-parametric tests were applied. Descriptive statistics were used to describe the personal characteristics of the subjects in both groups (the received treatment, age, sex, injured hand, hand dominance and fracture pattern). The researchers used the Chi-Square test for categorical variables and the Mann-Whitney U test for numeric variables, when comparing parameters between groups. Significance was set at $p < 0.05$.

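### Do 12 sessions, 2-3 a week and 6-8 weeks conflict in a way that makes the treatment length and final evaluation unusable?

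*Protocol*

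**What the plan says.** The second paragraph of the Study Protocol gives one schedule for both groups: all subjects "received 12 therapy sessions, 30 minutes each one, 2-3 times a week, during 6-8 weeks following the removal of the cast". Home exercise is also common to both: "Both groups were instructed to exercise at home, 3 times a day, 10 minutes per exercise session". For the DTM group it adds that "The dart splint orthosis was fitted to the subjects in the DTM group on their first evaluation session" and that "this group was required to fill in a chart at the end of each practice session, throughout the intervention period". The end of follow-up is defined by an event and not by a date: "At the completion of the treatment, the subjects were reexamined by the same evaluator".

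In the SAP, first paragraph, "the researchers calculated the residual deficit in all of the parameters between the evaluation post treatment and the evaluation at baseline". The second paragraph compares the groups by Mann-Whitney U for numeric variables and Chi-Square for categorical ones. The descriptive variables it lists are "the received treatment, age, sex, injured hand, hand dominance and fracture pattern". Neither document gives the interval from cast removal to baseline or from baseline to the final evaluation, and neither mentions a delayed start or rescheduled visits.

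**The concern.** A session count, a weekly frequency and a duration are linked: any two fix the third. Here two of them are ranges, and at a steady rate the three meet only at one corner. A reader could fairly ask how long treatment lasted.

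Two things depend on the answer. First, the outcome evaluation is tied to the end of treatment, so a loose duration means a loose measurement time. Patients are expected to improve after a cast comes off, so the baseline-to-post percentages depend partly on the time elapsed. Second, home exercise accumulates with duration, and the DTM orthosis was prescribed for use at home. If the groups had finished at different times, the comparison could mix a timing difference with a treatment difference.

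**Working it through.** **Inputs** (Study Protocol, second paragraph): 12 sessions; 30 minutes each; 2-3 a week; 6-8 weeks after cast removal; home exercise 3 times a day, 10 minutes each time.

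**Reproducing the stated count.** Sessions = frequency × weeks.

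| | 6 weeks | 7 weeks | 8 weeks |
|---|---|---|---|
| 2 a week | 12 | 14 | 16 |
| 3 a week | 18 | 21 | 24 |

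The stated 12 appears once, at 2 a week for 6 weeks.

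**Solving the other ways.**
- Weeks = sessions / frequency: 12/3 = 4 and 12/2 = 6, so 4-6 weeks.
- Frequency = sessions / weeks: 12/8 = 1.5 and 12/6 = 2, so 1.5-2 a week.
- Mixing weeks of 2 and 3 sessions to total exactly 12: four 3s (4 weeks), three 2s plus two 3s (5 weeks), or six 2s (6 weeks). None reaches 7 or 8 weeks.

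**The alternative reading.** Take the 6-8 weeks as a window counted from cast removal. The sessions need 4-6 weeks. The slack for a late start or missed visits runs from 6 − 6 = 0 weeks to 8 − 4 = 4 weeks. It is never negative, so nothing conflicts.

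**What depends on the reading.**
- Supervised time: 12 × 30 = 360 minutes = 6 hours. This does not vary, because both the count and the session length are stated as delivered.
- Time to final evaluation: about 4-6 weeks from the first session if count and frequency govern; 6-8 weeks if the stated period governs. The two ranges should not be joined into 4-8 weeks: they come from different readings, and the 6-8 weeks is counted from cast removal.
- Home exercise, assuming it is done daily for the whole treatment period (the Protocol does not say so): 3 × 7 × 4 = 84 sessions (840 minutes, 14 hours); 3 × 7 × 6 = 126 (1,260 minutes, 21 hours); 3 × 7 × 8 = 168 (1,680 minutes, 28 hours). That is 14-21 hours on the first reading and 21-28 hours on the second, with the same prescription in each group.

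**Effect on the comparison.** The SAP compares subject-level values between groups. If evaluation times vary from subject to subject in the same way in both groups, the spread within groups widens and some power is lost. A shift between groups requires the timing to differ by group. The documents contain nothing that shows such a difference, and no recovery rate, standard deviation or completion times from which to size the effect.

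**The case for a change.** The best case for a change is that it would be cheap and informative. One sentence could say how the three figures relate. If dates are on file, which neither document states, intervals by group would show whether timing was balanced, something the present text cannot show. The objection can add that the window reading is an inference, since the Protocol mentions no delay or gap, and that prescribed home practice, including orthosis use in the DTM group, depends on the duration.

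Part of this stands. The schedule is loosely written, the window is not identified as one, and a reader cannot recover the exact evaluation week. The three figures would need to be reconciled in any restatement; this review takes no view on which of them governs.

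What does not stand is the step from loose wording to a fault in the analysis. The possible imbalance is a conjecture, and the shared schedule gives it no support. The number of sessions is not in doubt, because the text reports what every subject received. Both documents describe completed work in the past tense, so rewording would not alter what was done or when outcomes were measured.

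**Conclusion.** The arithmetic behind the question is right: at a steady rate over the full period, the figures agree only at 2 a week for 6 weeks. It does not establish an error, because the sentence has a natural reading under which 4-6 weeks of sessions fall within a 6-8 week window after cast removal.

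The remaining uncertainty is about 4-6 or 6-8 weeks to the final evaluation, depending on the reading, with supervised time fixed at 6 hours. It applies to both groups under one schedule. On the assumption that timing did not differ systematically between groups, which the documents neither contradict nor confirm, the consequence is some added scatter of a size that cannot be calculated from them. This is a descriptive gap of the kind that analysts fill when they report the delivered schedule. No endpoint, test or conclusion in the plan depends on closing it, so no change is called for.

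### Only the dart-throwing-motion group is charted and telephoned about home exercise, so monitoring differs between arms and a resulting practice gap could be neither seen nor separated from the programme's effect

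*Protocol*

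**What the plan says.** The first paragraph of the Protocol's Study Protocol section frames the contrast as one of wrist motion: the Sagittal group works mostly in the sagittal plane "while the research group activated the wrist also in the dart throwing motion (DTM) plane", using an orthosis.

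The second paragraph gives both arms the same prescribed dose. All subjects "received 12 therapy sessions, 30 minutes each one, 2-3 times a week, during 6-8 weeks following the removal of the cast". For home exercise: "Both groups were instructed to exercise at home, 3 times a day, 10 minutes per exercise session".

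The same paragraph then describes the DTM group's resisted home exercise with the orthosis and adds a recording duty: "In addition, this group was required to fill in a chart at the end of each practice session, throughout the intervention period". It continues: "The evaluator performed weekly phone calls to remind the DTM group to fill these out". The Sagittal home programme follows: "The Sagittal group was instructed to perform at home active wrist motion similar to that practiced during the supervised therapy sessions". Neither a chart nor a call is mentioned for that group.

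The second paragraph of the SAP gives the group comparison: "The researchers used the Chi-Square test for categorical variables and the Mann-Whitney U test for numeric variables, when comparing parameters between groups". It names no adherence variable and no adjustment.

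**The concern.** Charting and weekly telephone contact are not features of any plane of motion. Either could be given to Sagittal subjects without altering their exercises, or withheld from DTM subjects without altering theirs. As written, they form a removable co-intervention that goes to one arm only.

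What is at stake is interpretation. Keeping a log after each session and expecting a weekly call about it may change how much home exercise is done. If it does, and if the amount of practice affects range of motion, pain or function, part of any difference between the groups reflects monitoring rather than the DTM exercises. A clinic that adopts the orthosis without the chart and calls might then not reproduce the result. Because home practice is recorded in one arm only, no later analysis can show whether this happened.

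**Working it through.** **1. The arms side by side (Study Protocol, second paragraph)**

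| Feature | DTM group | Sagittal group |
|---|---|---|
| Supervised dose | 12 x 30 min | 12 x 30 min |
| Home dose | 3 x 10 min a day | 3 x 10 min a day |
| Home exercise | Resisted, with orthosis | Active motion; no resistance mentioned |
| Chart after each home session | Required | None described |
| Weekly call about the chart | Yes | None described |

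The prescribed dose is equal. Monitoring is not.

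**2. How much of the dose is unsupervised**

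Days per week of home exercise are not stated; I assume 7 and show 5 for comparison. The course is taken as the stated 6 to 8 weeks. (Twelve sessions at 2 to 3 a week would take 12/3 = 4 to 12/2 = 6 weeks, so the two statements agree only at 6.)

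- Supervised: 12 x 30 = 360 min.
- Home, 7 days a week: 30 x 7 x 6 = 1,260 min; 30 x 7 x 8 = 1,680 min.
- Home share: 1,260/(1,260 + 360) = 77.8%; 1,680/(1,680 + 360) = 82.4%.
- At 5 days a week: 900/1,260 = 71.4% (6 weeks); 1,200/1,560 = 76.9% (8 weeks).
- Monitoring load per DTM subject at 7 days: 3 x 7 x 6 = 126 to 3 x 7 x 8 = 168 chart entries, and about 6 to 8 calls.

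**3. What an adherence gap would mean in minutes (gap assumed)**

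- 10 percentage points: 0.10 x 1,260 = 126 min to 0.10 x 1,680 = 168 min.
- 60% against 80%: 0.20 x 1,260 = 252 min to 0.20 x 1,680 = 336 min. Total exercise is then (360 + 1,008)/(360 + 756) = 1.23 times as much at 6 weeks, and (360 + 1,344)/(360 + 1,008) = 1.25 times at 8 weeks.

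**4. Can the planned analysis detect or separate a gap?**

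No. The Chi-Square and Mann-Whitney tests compare whole groups. Separating practice from programme would need practice data in both arms, and only the DTM arm has a chart.

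**5. Illustration of the consequence**

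The documents give no sample size, adherence level or practice-outcome relation, so every input here is assumed. Outcome = r x standardised adherence + noise, within-arm SD 1; no effect of the DTM exercises; DTM adherence shifted by k SD; two-sided Mann-Whitney test at 0.05; 20,000 simulated trials per cell. The implied outcome shift is r x k.

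| r | k | Shift (SD) | Rejects, 15 per arm | Rejects, 30 per arm |
|---|---|---|---|---|
| 0.2 | 0.4 | 0.08 | 5.0% | 5.9% |
| 0.2 | 0.8 | 0.16 | 6.5% | 8.6% |
| 0.4 | 0.4 | 0.16 | 6.2% | 8.9% |
| 0.4 | 0.8 | 0.32 | 12.1% | 21.9% |

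With r = 0 the rate is 4.3% to 5.1%. Imposing shifts of 0.2, 0.5 and 0.8 SD directly (4,000 trials per cell) gives about 7%, 15% and 35% with 10 per arm, and 10%, 44% and 84% with 30 per arm. The results run from no inflation to severe inflation according to what is assumed, so they show that the problem can occur, not how large it is in this trial.

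**The case against.** The strongest reply is that the mechanism is inferred. The calls are described as reminders about the charts, and a reader might infer that they were reminders to exercise. The documents do not say that, and they report no adherence difference. This stands as a limit on the claim. It does not remove the unequal monitoring, which is plain text.

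A reader might also infer that any bias must favour DTM. The documents do not support a direction. The DTM home task is resisted, needs a device and carries a recording burden, while Sagittal subjects repeat exercises familiar from their sessions. Without monitoring, DTM adherence might have been the lower of the two, in which case the chart and calls would narrow a gap rather than open one.

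A third point is that charting is not the only bundled difference: the orthosis and the resistance also go to one arm. That is correct. They belong to the DTM programme and I do not object to them, but they limit what equal monitoring can achieve.

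It might be added that the calls stand outside treatment because the evaluator makes them. The Protocol does not say whether the evaluator also treated subjects, so I place no weight on this. That subjects were "At the completion of the treatment, the subjects were reexamined by the same evaluator" raises a separate question of blinding, which this point does not need.

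Finally, both documents are written in the past tense, so equal monitoring may come too late for subjects already treated. For them only the claim can be changed.

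**Conclusion.** The concern holds as a design asymmetry that should be removed. One arm receives a chart and weekly contact, the other is described as receiving neither, and nothing in the SAP can detect or separate a resulting difference in practice. The home exercise exposed to this is about 78% to 82% of prescribed time, assuming 7 days a week over 6 to 8 weeks.

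That monitoring changes practice is plausible but inferred; whether it did, in which direction and by how much are unknown. The rejection rates should not be read as this trial's false-positive rate. Nor should a reader infer that equal monitoring would isolate motion plane: plane, orthosis and resistance would still differ together.

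**What to change.** - **Chart:** use the same home-exercise chart, completed after each session, in both groups.
- **Calls:** either make the same scripted weekly call to both groups or drop the calls in both. No additional caller is needed.
- **Analysis:** keep the planned unadjusted comparison by assigned group. Report charted sessions per week and the share of missing charts for each group. Treat a blank as missing, not as a session not done: the calls exist to get charts filled in, so an empty entry does not show that no exercise took place.
- **Wording:** describe the contrast as the DTM programme (plane, orthosis and resisted exercise) against active sagittal exercise under equal monitoring. For subjects already treated, describe it as the DTM package including charting and calls, and do not attribute a difference to motion plane alone.

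The cost is one chart per Sagittal subject and, if calls are kept, about 6 to 8 short calls each over the stated course. The downsides are that Sagittal home care is monitored more than now planned (DTM care less, if calls are dropped), and that charts are self-reported and may overstate practice.

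### On the natural reading, the evaluator who made weekly reminder calls to the DTM group only also did the final examination, and no safeguard against detection bias is given

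*Protocol*

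**What the plan says.** The second paragraph of the Protocol sets out the home programme and follow-up. On the DTM group it says "In addition, this group was required to fill in a chart at the end of each practice session, throughout the intervention period", and then "The evaluator performed weekly phone calls to remind the DTM group to fill these out". It describes neither a chart nor calls for the Sagittal group. The paragraph ends: "At the completion of the treatment, the subjects were reexamined by the same evaluator".

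On what was measured, the first paragraph of the Protocol says of the pretrial assessment that "upper limb range of motion (ROM), pain levels and functional tests were recorded by a hand therapist". The SAP forms a percentage change from baseline to post-treatment for its parameters. It adds: "For the pinch and grip strength tests, measured post treatment, the researchers calculated the percentages of the values of the injured hand", taken relative to the uninjured side. It does not say who took the strength measurements. Numeric variables are compared between groups by the Mann-Whitney U test.

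Neither document mentions blinding, masking, an independent assessor or any other step to keep the group from the person measuring outcomes.

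**The concern.** Subjects and treating therapists cannot be blinded to a splint-based exercise programme, but the person who measures the outcomes often can be. Here an administrative task, chasing completion of a chart, appears to have been given to that person, and for one group only. Whoever holds the call list knows who is in the DTM group and, by elimination, who is not.

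An examiner who knows the group can position a joint, encourage effort, accept or repeat a reading, or record a borderline value differently by group, without intending to. ROM is open to this, and so are any tests that the examiner scores. Comparing the two groups is the purpose of the study, so its conclusions on these outcomes depend on the measurements having been made alike in both.

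**Working it through.** The plan states no figure to reproduce. It gives no sample size, standard deviation or measurement error from which the size of a bias could be estimated. The check is therefore a reading of the statements side by side.

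1. **Who receives the calls.** The DTM group (Protocol, second paragraph). The chart that prompts the calls is described for that group only.
2. **Who makes the calls.** The evaluator (same paragraph).
3. **Who does the final examination.** The same evaluator (last sentence of that paragraph). The Protocol uses the word evaluator only twice, first for the caller and then for the final examiner. The natural reading is one person.
4. **What follows.** From 1 to 3, the final examiner knows who is in the DTM group. The knowledge comes from following the procedure as written. It does not need a subject's slip or a glimpse of the splint. A single call is enough to reveal the group, so the number of calls does not matter.
5. **Which outcomes are exposed.** The Protocol does not list what the re-examination covered. The SAP compares post-treatment with baseline values, so I assume that the baseline measures were repeated.
   - ROM is measured by an examiner and is exposed.
   - The functional tests are not named and their scoring is not described. They are exposed only so far as an examiner scores them.
   - Grip and pinch are exposed only if the evaluator took them.
   - I do not extend the point to pain, because the documents do not say how it was scored, or to the radiological measurements, because nothing connects the evaluator with them.
6. **Whether the analysis deals with it.** The SAP's change measure is 100 − (post / pre) × 100. If the recorded post value is shifted by an amount b, the measure becomes 100 − ((post + b) / pre) × 100, a change of −100 × b / pre. If b differs by group, that difference passes straight into the quantity compared. The Mann-Whitney test compares the values as recorded and cannot tell a shift in measurement from a shift due to therapy. No other step in the SAP addresses this.

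**The case against.** **The evaluator may be two people.** The baseline data were recorded by a hand therapist, so the final sentence could mean the baseline examiner and not the caller. This stands as an uncertainty. It is why the point is put as the natural reading and why the fix asks who did what. A reader might infer that the examiner's knowledge of the group is certain. The text makes it a direct inference, not a stated fact.

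**No bias has been shown.** Correct. A reader might infer that the results are biased, or biased towards DTM. The documents support neither. They show a route by which bias could enter.

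**The functional tests may be questionnaires.** Also fair. Their dependence on the examiner cannot be assumed, and the point is limited accordingly.

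**Further evidence that a reader might add.** Two items are tempting, and I rely on neither.

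- The Protocol says "The dart splint orthosis was fitted to the subjects in the DTM group on their first evaluation session", which could be read as a second way for the evaluator to learn the group. But the orthosis was applied by a hand therapist, and nothing says that the evaluator was present or in what order fitting and measurement took place. This would bear mainly on baseline, not on the final examination.
- The therapy schedule, "All of the subjects in both groups received 12 therapy sessions, 30 minutes each one, 2-3 times a week, during 6-8 weeks", could be used to count calls or to allege a contradiction. Twelve sessions at 2-3 per week take 12/3 = 4 to 12/2 = 6 weeks. The stated 6-8 weeks is tied to cast removal and can be read as a window that contains them. A contradiction is not shown, and the count does not affect the point.

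**The study seems to be over.** The past tense, the title's reference to preliminary results and the SAP's statement "The majority of variables were not normally-distributed so a-parametric tests were applied" suggest that most or all subjects have been assessed. For them the design cannot be changed, and only disclosure and narrower conclusions remain.

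**Conclusion.** The point holds as a risk of detection bias that the written procedure creates and that neither document guards against. It is more than a missing detail: on the natural reading, following the Protocol unblinds the final examiner. It applies to ROM, to the functional tests so far as they are examiner-scored, and to grip and pinch if the evaluator took them. Size and direction are unknown and cannot be derived from the documents.

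The conclusion rests on two assumptions: that the caller and the final examiner are the same person, and that the final examination repeated the baseline measures. If someone else made the calls, this route falls away, although the documents would still state no blinding. The point should be fixed. It does not by itself invalidate the between-group comparison.

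**What to change.** **(a) Subjects already assessed.** State who made the reminder calls, who took the final measurements (including grip and pinch), how the functional tests were scored, and whether the person measuring knew the group. If the examiner was unblinded, say so plainly and limit the between-group conclusions on the affected outcomes. If a different person made the calls, say that instead. The cost is a few sentences and more cautious conclusions.

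**(b) Subjects not yet assessed, and any further study.** Move the chart reminders from the evaluator to the treating hand therapists, at the 12 sessions that subjects already attend. Withhold the group from the evaluator, and ask subjects not to reveal it at the final examination. The cost is a few minutes of therapist time per subject, with no additional visit.

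Part (b) has limits. Subjects may still disclose their group, so blinding may be imperfect. The chart and reminders also remain extra attention given to one group. The documents do not say whether the evaluator also treats subjects. If so, moving the reminders does not blind the examination and the disclosure in (a) applies.
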